9.2 Safety Event Reporting Procedures

9.2.1 Reporting Procedures for Disease Related Events

The investigator is responsible for ensuring that all Disease Related Events (serious or nonserious) observed by the investigator or reported by the subject that occur after the first dose of talimogene laherparepvec through the safety follow-up visit (ie, 30 [+7] days after the last dose of talimogene laherparepvec), are reported using the Event CRF.

Additionally, the investigator is required to report a fatal disease related event on the event CRF as a Disease Related Event.

All serious disease related events will be recorded and reported to the sponsor or designee within 24 hours. The investigator will submit any updated serious disease related event data to the sponsor within 24 hours of it being available.

The investigator must assign the following attributes to each disease related event:

- disease related event diagnosis or syndrome(s), if known (if not known, signs or symptoms),
- dates of onset and resolution (if resolved),
- severity (and/or toxicity per protocol),
- assessment of relatedness to talimogene laherparepvec, and
- action taken

CTCAE version 4.0 will be used to grade a disease related event. The grading scale used in this study is described in [Appendix A](#).

Note: If the event is more severe than expected for the subject's condition or if the investigator believes there is a causal relationship between the investigational product(s)/study treatment/protocol required therapies and disease worsening, the event should be reported as an adverse event, not a disease related event.

The investigator is expected to follow reported disease related events (serious or non-serious) until stabilization or reversibility.

9.2.2 Adverse Events

9.2.2.1 Reporting Procedures for Adverse Events That Do Not Meet Serious Criteria

The investigator is responsible for ensuring that all adverse events observed by the investigator or reported by the subject that occur after first dose of talimogene laherparepvec through the safety follow-up visit (ie, 30 [+7] days after the last dose of talimogene laherparepvec) are reported using the Event CRF. **Additionally, talimogene laherparepvec related adverse events that occur after the safety follow-up visit through the end of the long-term follow-up will be reported.**

The investigator must assign the following attributes to each adverse event:

- Adverse event diagnosis or syndrome(s), if known (if not known, signs or symptoms),
- Dates of onset and resolution (if resolved),
- Severity (and/or toxicity per protocol),
- Assessment of relatedness to talimogene laherparepvec and,
- Action taken.

The adverse event grading scale used will be the CTCAE version 4.0. The grading scale used in this study is described in [Appendix A](#). The investigator must assess whether the adverse event is possibly related to the talimogene laherparepvec. This relationship is indicated by a “yes” or “no” response to the question: Is there a reasonable possibility that the event may have been caused by the investigational product(s)?

The investigator is responsible for reviewing laboratory test results and determining whether an abnormal value in an individual study subject represents a clinically significant change from the subject's baseline values. In general, abnormal laboratory findings without clinical significance (based on the investigator's judgment) are not to be recorded as adverse events. However, laboratory value changes that require treatment or adjustment in current therapy are considered adverse events. Where applicable, clinical sequelae (not the laboratory abnormality) are to be recorded as the adverse event.

The investigator is expected to follow reported adverse events until stabilization or reversibility.

9.2.2.2 Reporting Procedures for Serious Adverse Events

The investigator is responsible for ensuring that all serious adverse events observed by the investigator or reported by the subject that occur after signing of the informed consent through 90 (+ 7) days after the cessation of all study treatment, or 30 (+7) days following cessation of treatment if the subject initiates new anticancer therapy, whichever is earlier, are recorded in the subject's medical record and are submitted to Amgen/AABP. Additionally, talimogene laherparepvec related serious adverse events that occur after the safety follow-up visit through the end of the long-term follow-up will be reported. Any serious adverse event, or follow-up to a serious adverse event, including death due to any cause other than progression of the cancer under study (refer to [Section 9.1.3](#) for additional details) that occurs to any subject must be reported within 24 hours to Amgen/AABP including serious adverse events that cause the subject to be excluded from the trial, or is the result of a protocol-specified intervention, including but not limited to washout or discontinuation of usual therapy, diet, placebo treatment, or a procedure.

If the electronic data capture (EDC) system is unavailable to the site staff to report the serious adverse event, the information is to be reported to Amgen/AABP via an electronic Adverse Event Contingency Report Form within 24 hours of the investigator's knowledge of the event. See [Appendix B](#) for a sample of the electronic Adverse Event Contingency Report Form. The data must be entered into the EDC system when the system is again available.

The investigator must assess whether the serious adverse event is possibly related to any study-mandated activity or procedure. This relationship is indicated by a "yes" or "no" response to the question: "Is there a reasonable possibility that the event may have been caused by a study activity/procedure"?

The investigator is expected to follow reported serious adverse events until stabilization or reversibility.

All new information relating to a previously reported serious adverse event must be submitted to Amgen/AABP within 24 hours following knowledge of the new information. The investigator may be asked to provide additional follow-up information, which may include a discharge summary or extracts from the medical record. Information provided about the serious adverse event must be consistent with that recorded on the Event CRF.

If a subject is permanently withdrawn from protocol-required therapies because of a serious adverse event, this information must be submitted to Amgen/AABP.

Amgen/AABP will report serious adverse events and/or suspected unexpected serious adverse reactions as required to regulatory authorities, investigators/institutions, and IEC/IRBs in compliance with all reporting requirements according to local regulations and GCP.

The investigator is to notify the appropriate IEC/IRB of serious adverse events occurring at the site and other adverse event reports received from Amgen/AABP, in accordance with local procedures and statutes.

9.2.2.3 Reporting Serious Adverse Events After the Protocol-required Reporting Period

There is no requirement to monitor study subjects for serious adverse events following the protocol-required reporting period or after end of study. However, these serious adverse events can be reported to Amgen/AABP. In some countries (eg, European Union [EU] member states), investigators are required to report serious adverse events that they become aware of after end of study. If serious adverse events are reported, the investigator is to report them to Amgen/AABP within 24 hours following the investigator's knowledge of the event.

Serious adverse events reported outside of the protocol-required reporting period will be captured within the safety database as clinical trial cases for the purposes of expedited reporting.

9.3 Pregnancy and Lactation Reporting

If a female subject becomes pregnant, or a male subject fathers a child, while the subject is taking talimogene laherparepvec report the pregnancy to Amgen/AABP Global Patient Safety as specified below.

In addition to reporting any pregnancies occurring during the study, investigators should report pregnancies that occur after the last dose of talimogene laherparepvec through 3 months after the last dose of talimogene laherparepvec.

The pregnancy should be reported to Amgen's Global Patient Safety within 24 hours of the investigator's knowledge of the event of a pregnancy. Report a pregnancy on the Pregnancy Notification Worksheet ([Appendix C](#)). Amgen Global Patient Safety will follow-up with the investigator regarding additional information that may be requested.

If a female subject becomes pregnant during the study, the investigator should attempt to obtain information regarding the birth outcome and health of the infant. If a male subject's female partner becomes pregnant, the investigator should discuss obtaining information regarding the birth outcome and health of the infant from the pregnant partner.

If the outcome of the pregnancy meets a criterion for immediate classification as a Serious Adverse Event (eg, female subject experiences a spontaneous abortion, stillbirth, or neonatal death or there is a fetal or neonatal congenital anomaly) the investigator will report the event as a Serious Adverse Event.

If a female breastfeeds while taking talimogene laherparepvec report the lactation case to Amgen/AABP as specified below.

In addition to reporting a lactation case during the study, investigators should report for lactation cases that occur after the last dose of protocol-required therapies through 3 months after the last dose of talimogene laherparepvec.

Any lactation case should be reported to Amgen's Global Patient Safety within 24 hours of the investigator's knowledge of event. Report a lactation case on the Lactation Notification Worksheet ([Appendix C](#)). Amgen Global Patient Safety will follow-up with the investigator regarding additional information that may be requested.

9.4 Reporting of Exposure to Talimogene Laherparepvec

If a household member, caregiver, or healthcare provider who has had close contact with a subject treated with talimogene laherparepvec on this study is suspected to have been exposed to talimogene laherparepvec (eg, have or who have had signs or symptoms suspected to be herpetic in origin or who have been accidentally exposed to talimogene laherparepvec), while the subject is taking talimogene laherparepvec, report the exposure to Amgen/AABP as specified below. In addition to reporting an unintended exposure case during the study treatment, investigators should monitor for potential exposure cases that occur after the last dose of talimogene laherparepvec through 30 (+7) days after the last dose of talimogene laherparepvec.

Any potential or known unintended exposure should be reported to Amgen/AABP within 24 hours of the investigator's knowledge of the event of exposure. Amgen/AABP will seek to follow-up with the exposed individual, if necessary, to collect more information about the exposed individual contact with clinical trial subject, signs and/or symptoms related to the exposure, medical history, and/or outcome of the exposure. If the exposed

individual is reporting sign or symptoms suspected to be related to talimogene laherparepvec exposure, the exposed individual may be asked to have a swab taken to evaluate for the presence of talimogene laherparepvec in the lesion within 3-days of the symptoms or signs occurring.

Report the herpes-related events on Clinical Trial Report of Suspected Talimogene Laherparepvec Associated Adverse Event for Health Care Professional (HCP) or Close Contact ([Appendix F](#)). Amgen Global Patient Safety will follow-up with the investigator regarding additional information that may be requested.

10. STATISTICAL CONSIDERATIONS

10.1 Study Endpoints, Analysis Sets, and Covariates

10.1.1 Study Endpoints

10.1.1.1 Primary Endpoints

- Subject incidence of DLTs
- DRR using modified WHO response criteria by investigators

10.1.1.2 Secondary Endpoints

- ORR, TTR, DOR, and PFS using modified WHO response criteria by investigators
- OS

10.1.1.3 Safety Endpoint

- Subject incidence of all the following, where not defined as DLT:
 - adverse events
 - grade ≥ 3 adverse events
 - serious adverse events
 - clinically significant laboratory changes
 - changes in vital signs

10.1.1.4 Analysis Sets

10.1.1.4.1 DLT Analysis Set

The DLT analysis set will include DLT-evaluable subjects as defined in [Section 6.2.1.2.2](#).

10.1.1.4.2 Safety Analysis Set

The safety analysis set will include all subjects who received at least 1 dose of talimogene laherparepvec.

10.1.1.4.3 Covariates and Subgroups

The following covariates will be used to examine efficacy and safety in subgroups or in multivariate analyses as appropriate:

- Age at baseline: < 50, \geq 50; < 65, \geq 65; < 75, \geq 75 years
- Sex (female vs male)
- Disease stage at baseline: IIIB and IIIC vs IVM1a vs IVM1b vs IVM1c
- Line of therapy for current disease
- Type of prior therapy
- Baseline HSV-1 serostatus
- Baseline LDH \leq ULN vs $>$ ULN
- ECOG (0 vs 1)

10.2 Sample Size Considerations

10.2.1 Sample Size Considerations

The total number of subjects that will participate in the study is approximately 18.

10.2.1.1 Sample Size Considerations for Safety Evaluation

In the current study, a dose level will be considered safe if there are 0 to 1 DLTs observed in the initial 6 DLT evaluable subjects. [Table 4](#) and [Figure 1](#) presents the probability of declaring a dose level safe (unsafe) for a range of true DLT rates for the protocol therapy for the 6 DLT-evaluable subjects (see triangle symbols). As shown below in [Table 4](#), the probability of declaring a dose level safe (unsafe) in the current study (based on only 6 DLT evaluable subjects) is 89% (11%), 42% (58%), and 11% (89%) if the true DLT rate is 10%, 30%, or 50%, respectively. Hypothetically, if the study were to enroll an additional 6 DLT-evaluable subjects after the initial 6 subjects (total of 12 DLT evaluable subjects), the probability of observing a DLT rate \geq 33% in the 12 subjects following the observation of 0-1 DLTs in the first 6 DLT evaluable subjects would be 0.6%, 8.6%, and 6.7% if the true DLT rate is 10%, 30%, or 50%, respectively.

Figure 1. Probability of Declaring a Cohort Safe (Unsafe)

[figure not shown]

Table 4. Probability of Declaring a Cohort Safe or Unsafe

True Cohort DLT Probability	Probability Declare Cohort Safe	Probability Declare Cohort Unsafe
10%	89%	11%
20%	66%	34%
30%	42%	58%
40%	23%	77%
50%	11%	89%

DLT= dose-limiting toxicity

10.2.1.2 Sample Size Considerations for Efficacy

A 1-sided 5% significance level exact binomial test will be performed to test the null hypothesis of a 2% DRR. The expectation is that this test will be based on the first 18 subjects that receive at least 1 dose of talimogene laherparepvec. The null hypothesis will be rejected if at least 2 subjects achieve a durable response

(DR). Assuming a DRR of 16.3% consistent with the global phase 3 study, this analysis will have 81% power.

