Hypotheses:

No formal statistical hypothesis will be tested for safety endpoints in this trial. Based on the well tolerated safety profile from a global phase 3 study, it is hypothesized that talimogene laherparepvec will be safe and well tolerated in Japanese subjects with unresectable stage IIIB-IVM1c malignant melanoma. A DRR is hypothesized to be consistent with results from the global phase 3 study.

Primary Endpoint(s):

- Subject incidence of DLTs
- DRR using modified WHO response criteria by investigators

Secondary Endpoint(s):

- ORR, TTR, DOR, and PFS using modified WHO response criteria by investigators
- OS

Study Design:

This is a phase 1, multicenter, open-label study of talimogene laherparepvec in Japanese subjects with unresectable stage IIIB-IV malignant melanoma who are candidates for intralesional therapy. Up to approximately 18 subjects will be enrolled in the study. Subjects may be included in the evaluation for both safety and efficacy. The DLT evaluation period is 35 days from the initial administration of talimogene laherparepvec. Initially, 6 DLT-evaluable subjects will be

enrolled and treated at Dose 1 (up to 4.0 mL of 10^6 PFU/mL talimogene laherparepvec will be administered on day 1, followed by a dose of up to 4.0 mL of 10^8 PFU/mL 3 weeks [\pm 5 days] later and then up to 4.0 mL of 10^8 PFU/mL every 2 weeks [\pm 3 days] thereafter). Upon demonstration of safety based on DLT rules, an additional 12 subjects will be enrolled and treated at Dose 1 to obtain additional safety data. If dose de-escalation is needed based on the DLT evaluation of the first 6 DLT-evaluable subjects, then an additional 6 subjects will be treated at Dose -1 (up to 4.0 mL of 10^6 PFU/mL talimogene laherparepvec will be administered on day 1, followed by dose of up to 4.0 mL of 10^7 PFU/mL 3 weeks [\pm 5 days] later and then up to 4.0 mL of 10^7 PFU/mL every 2 weeks [\pm 3 days] thereafter). The same DLT rules will be used to evaluate safety based on the initial 6 DLT-evaluable subjects after dose de-escalation. Upon demonstration of safety, additional subjects will be enrolled (up to a total of 18 subjects) at Dose-1 to obtain additional safety data. The hypothesis test for DRR will include all subjects enrolled after dose de-escalation who received at least 1 dose of talimogene laherparepvec. If no dose de-escalation is needed the DRR hypothesis test will include the first 18 subjects dosed.

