3. EXPERIMENTAL PLAN

3.1 Study Design

This is a phase 1, multicenter, open-label study of talimogene laherparepvec in Japanese subjects with unresectable stage IIIB-IVM1c malignant melanoma that are candidates for intralesional therapy.

Approximately 18 subjects will be enrolled in the study. Subjects may be included in the evaluation for both safety and efficacy. The DLT evaluation period is 35 days from the initial administration of talimogene laherparepvec. Initially, 6 DLT-evaluable subjects will be enrolled and treated at 100% of the dose regimen of talimogene laherparepvec (Dose 1) as described below. The first dose administered will be up to 4.0 mL of 10^6 PFU/mL (day 1, week 0) followed by dose of up to 4.0 mL of 10^8 PFU/mL 3 weeks (+ 5 days) later. Subsequent doses of up to 4.0 mL of 10^8 PFU/mL will be administered every 2 weeks (\pm 3 days) thereafter (see [Section 6.2.1.1](#)). A Dose Level Review Team (DLRT) meeting will be convened after 6 DLT-evaluable subjects are enrolled. Further enrollment will be temporarily paused until the DLRT meeting is convened and a decision is made on the dose level. Upon demonstration of safety based on DLT incidence < 33% in the first 6 subjects, an additional 12 subjects will be enrolled and treated at Dose 1 to obtain additional safety data.

However, if at any time there are 2 or more subjects with a DLT prior to enrollment of the first 6 DLT-evaluable subjects, an ad hoc DLRT meeting will be convened to determine if dose de-escalation is required.

The safety data during the enrollment of the additional 12 subjects will be monitored on an ongoing basis and an ad hoc DLRT meeting may be called, if needed, to determine the further course of the study.

The hypothesis test for DRR will include all subjects enrolled after dose de-escalation who received at least 1 dose of talimogene laherparepvec. If no dose de-escalation is needed, the DRR hypothesis test will include the first 18 subjects dosed.

Dose De-escalation

If dose de-escalation is needed then the remaining subjects will be treated at the lower dose regimen of talimogene laherparepvec (Dose -1). The initial dose administered will be up to 4.0 mL of 10^6 PFU/mL (day 1, week 0) followed by dose of up to 4.0 mL of 10^7 PFU/mL 3 weeks (+ 5 days) later. Subsequent doses of up to 4.0 mL of 10^7 PFU/mL will be administered every 2 weeks (\pm 3 days) thereafter (see [Section 6.2.1.2](#)). The

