6.2.1.2 Dose-cohort Study De-escalation and Stopping Rules

6.2.1.2.1 Rules for DLT Evaluation

The DLT evaluation period is 35 days from the first dose of talimogene laherparepvec. To be evaluable for a DLT, subjects must have received at least 1 dose of talimogene laherparepvec and had the opportunity to be followed for the entire DLT evaluation period or have experienced a DLT within the DLT evaluation period. To obtain the first 6 DLT-evaluable subjects, subjects will be replaced if they are not evaluable for DLT (eg, a subject did not receive study treatment, or ended the study treatment before completion of DLT evaluation period for a reason other than experiencing a DLT).

A DLRT composed of the investigator(s), Amgen Medical Monitor, Amgen Global Safety Officer or designated safety scientist, Amgen Clinical Research Study Manager and Amgen Biostatistics representative will review data, monitor safety, and make dose and dose de-escalation decisions. Additional members may be added to the DLRT as needed (eg, Global Development Leader) (see [Section 10.3.2](#)). The DLRT will review the safety data after 6 DLT-evaluable subjects have been enrolled at Dose 1 (see below). Enrollment will be temporarily paused during the DLT review period to evaluate the 6 DLT-evaluable subjects. The decision to continue to enroll 12 additional subjects at the Dose 1 will be based on observing < 33% subject incidence of a DLT in the initial 6 subjects during the DLT evaluation period.

If at any time there are 2 or more subjects with a DLTs prior to enrollment of the first 6 DLT-evaluable subjects, an ad hoc DLRT meeting will be convened to determine if dose de-escalation (Dose -1) is required. The safety data during the enrollment of the additional subjects will be monitored on an going basis and an ad hoc DLRT meeting may be called, if needed, to determine the further course of the study.

Dose De-escalation

If dose de-escalation is needed, then the remaining subjects will be treated at the lower dose regimen of talimogene laherparepvec (Dose -1).

Dose	Initial dose	Subsequent doses
1	10^6 PFU/mL (day 1, week 0)	10^8 PFU/mL (3 weeks later and then every 2 weeks thereafter)
-1	10^6 PFU/mL (day 1, week 0)	10^7 PFU/mL (3 weeks later and then every 2 weeks thereafter)

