Dose -1 will be administered as an initial dose up to 4.0 mL of 10^6 PFU/mL (day 1, week 0) followed by dose of up to 4.0 mL of 10^7 PFU/mL 3 weeks later (+ 5 days). Subsequent doses of up to 4.0 mL of 10^7 PFU/mL will be administered every 2 weeks (\pm 3 days) thereafter.

The DLRT will review the safety data after the first 6 DLT-evaluable subjects at Dose -1 have been enrolled. Enrollment will be temporarily paused during the DLT review period to evaluate the 6 DLT-evaluable subjects at Dose -1. Upon demonstration of safety, additional subjects will be enrolled (up to a total of 18 subjects) at Dose -1 to obtain additional safety data.

The safety data of the subjects enrolled at the Dose-1 level will be monitored on an ongoing basis and an ad hoc DLRT meeting may be called, if needed, to determine the further course of the study.

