10.3.2 Dose Level Review Team

DLRT meetings will be held to review data, monitor safety, and make dose and dose de-escalation decisions. The review team will be composed of the investigator(s), Amgen Medical Monitor, Amgen Global Safety Officer or designated safety scientist, Amgen Clinical Research Study Manager and Amgen Biostatistics representative. Additional members may be added as needed (eg, Global Development Leader). A quorum, defined as > 50% of the participating investigators or their qualified designee [ie, sub-PI or research nurse or study coordinator possessing hard copy documentation (eg, email) of the PI's vote regarding the dose level review], must be in attendance for DLRT. The DLRT will be rescheduled if a quorum is not reached. The DLRT members are responsible for dosing decisions, which may include dose de-escalation, continuation, delay, or termination of dosing. All available study data, including demographics, investigational product administration, medical history, concomitant medications, adverse events, ECGs, vital signs, laboratory results will be reviewed. In addition to DLTs, all \geq grade 3 toxicities not meeting DLT criteria will be reviewed by the team and can be considered in the DLRT's decisions. Data to be reviewed will be queried.

The DLRT will review the safety data after the first 6 DLT-evaluable subjects have been enrolled. The DLRT will recommend either to declare the current dose intolerable (if 2 or more DLTs observed among the first 6 subjects), or to declare the dose safe and enroll 12 additional subjects (if 0 to 1 DLTs observed among first 6 subjects).

The decision to enroll additional subjects at the same dose will be based on observing < 33% subject incidence of a DLT.

If at any time there are 2 or more subjects with a DLT prior to enrollment of the first 6 DLT-evaluable subjects, an ad hoc DLRT meeting will be convened to determine if dose de-escalation is required.

If dose de-escalation is required, the DLRT will review the safety data after the first 6 DLT-evaluable subjects at Dose -1 have been enrolled.

The safety data of the subjects enrolled beyond the DLT evaluable period at the Dose-1 level will be monitored on an ongoing basis and an ad hoc DLRT meeting may be called, if needed, to determine further course of the study.

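### Does the 81% power for durable response rate mislead because no sample size or power is given after dose de-escalation?

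*Protocol*

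**What the plan says.** Protocol section 10.2.1.2 sets a one-sided 5% exact binomial test of a 2% DRR, rejected with 2 or more durable responders. It describes the set tested as follows: "The expectation is that this test will be based on the first 18 subjects that receive at least 1 dose of talimogene laherparepvec". It then adds "Assuming a DRR of 16.3% consistent with the global phase 3 study, this analysis will have 81% power". Section 10.4.2 and the synopsis repeat this. SAP section 3.2 and Table 2 give 81.7% for 18 subjects, and both restrict the figure to the case without de-escalation.

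For the other branch, protocol section 3.1 says "The hypothesis test for DRR will include all subjects enrolled after dose de-escalation who received at least 1 dose of talimogene laherparepvec". SAP section 3.2 calls this the safety analysis set at Dose -1, and SAP section 10.5 applies the same one-sided 5% exact test to it. No number or power is attached.

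On enrolment, the synopsis says "Up to approximately 18 subjects will be enrolled in the study" and section 10.2.1 says "The total number of subjects that will participate in the study is approximately 18". Section 6.2.1.2.1 says "If dose de-escalation is needed, then the remaining subjects will be treated at the lower dose regimen" and, once the first 6 at that level are judged safe, "additional subjects will be enrolled (up to a total of 18 subjects) at Dose -1".

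**The concern.** DRR is a co-primary endpoint and carries the study's only formal test. De-escalation is in the study's title, and protocol Table 4 puts the chance of declaring Dose 1 unsafe at 11% for a true DLT rate of 10% and at 34% for 20%. A reader who takes 81% as the power of the trial would be wrong on that branch.

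The number tested there cannot be read off with certainty. The ceiling of 18 could be the study total or the Dose -1 total. With 6 subjects already treated at Dose 1, it cannot be both. An early decision is also possible: section 10.3.2 calls an ad hoc review in this case: "If at any time there are 2 or more subjects with a DLT prior to enrollment of the first 6 DLT-evaluable subjects". Replacement of non-evaluable subjects (section 3.4) moves the number again. At stake is a fall in power of about 21 percentage points that the protocol does not show.

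**Working it through.** **Inputs.** Null DRR 2%, alternative 16.3%, rejection at 2 or more responders, 18 tested (protocol 10.2.1.2). First cohort of 6 DLT-evaluable subjects (protocol 3.1). The 16.3% comes from the phase 3 study, which used the 10^8 PFU/mL regimen (protocol 2.2). The documents give no DRR for Dose -1, so using 16.3% there is an assumption.

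**Formula.** With n tested and true rate p, the chance of rejecting is P(X ≥ 2) = 1 − (1 − p)^n − n·p·(1 − p)^(n−1).

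**The plan's own figure, n = 18.**
- Error: 1 − 0.98^18 − 18 × 0.02 × 0.98^17 = 1 − 0.6951 − 0.2554 = 0.0495.
- Power: 1 − 0.837^18 − 18 × 0.163 × 0.837^17 = 1 − 0.0407 − 0.1425 = 0.8169.

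This reproduces the 5.0% and 81.7% in SAP Table 2 and supports the protocol's 81%.

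**Number tested after de-escalation.**
- 18 as the study total: 18 − 6 = 12 after a full Dose 1 cohort. If an ad hoc review led to de-escalation after 5 down to 2 subjects, 18 − 5 = 13 up to 18 − 2 = 16.
- Enrolment stopped after the first cohort at Dose -1: 6.
- 18 as the Dose -1 total: 18 tested, with 18 + 6 = 24 enrolled after a full Dose 1 cohort, and more if any were replaced.

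**The same formula at those sizes, cut-off 2.**

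| n tested | One-sided error at 2% | Power at 16.3% |
|---|---|---|
| 6 | 0.6% | 25.4% |
| 12 | 2.3% | 60.5% |
| 14 | 3.1% | 69.1% |
| 16 | 4.0% | 76.1% |
| 18 | 4.95% | 81.7% |

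For n = 12 in full: power = 1 − 0.837^12 − 12 × 0.163 × 0.837^11 = 1 − 0.1182 − 0.2763 = 0.6055.

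**Cut-off.** A cut-off of 1 would not do at these sizes: even at n = 6, 1 − 0.98^6 = 11.4%, above 5%. So 2 is the exact 5% cut-off from 6 to 18. It first fails at 19, where the error is 5.46%, and the ceiling of 18 keeps the Dose -1 set below that on either reading.

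**Which total.** The synopsis limits enrolment in the study to about 18, section 10.2.1 says the same of participation, and section 6.2.1.2.1 sends the subjects who remain to the lower level. All three fit 18 as the study total. Reading it as the Dose -1 total would put about 24 in the study, against those statements.

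**The case for a change.** The strongest reply is that SAP section 3.2 justifies 18 by power: Table 2 shows it giving the most power between 16 and 20 subjects, against a target of 80%. Having chosen the size that way, the plan should say what power is left on a branch it provides for. If 18 is plainly the study total, the figure of about 60% was available and was not printed. At 12 tested, a true DRR of 16.3% would be missed 39.5% of the time (100 − 60.5), against 18.3% at 18 (100 − 81.7).

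The omission is real, and so is the loose wording of the ceiling. But the branch is less likely, and its power less definite, than this suggests. The 11% and 34% depend on assumed DLT rates, and the protocol expects the product to be well tolerated. At a 5% rate (an assumption) the chance of 2 or more DLTs in 6 is 1 − 0.95^6 − 6 × 0.05 × 0.95^5 = 3.3%. The ad hoc review decides whether to de-escalate, so sizes of 13 to 16 are a further contingency. Any power printed for Dose -1 would rest on a DRR the documents do not supply: over the phase 3 interval of 12% to 21%, power at 12 tested runs from 43% to 75%.

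**Conclusion.** No change is needed. The stated power is correct, and the documents limit it to the case it describes, the SAP expressly and the protocol through its reference to the first 18 dosed. On the de-escalation branch the analyst knows whom to include, which test to run and at what level. The cut-off of 2 holds the error at or below 5% at every size from 6 to 18, so neither reading of the enrolment ceiling threatens a false positive.

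The cost of the branch is lower power: about 60.5% at 12 tested and 25.4% if enrolment stops at 6, both assuming 16.3% at Dose -1. That follows from a small phase 1 study spending subjects on a dose it then leaves, and printing the number would not recover it. Power plays no part in the analysis once data are in. The result will be read from the count of responders, the number tested and the exact 90% and 95% intervals in protocol section 10.4.2. The enrolment wording is ambiguous, not contradictory, because taking 18 as the study total fits all of it.
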